11.1.1.4 Risks Associated with the Recharging System

The recharger, antenna, and belt are not sterile, and contact with the wound could cause an infection. The recharger is not intended to be used on an unhealed wound.

Use of rechargeable neurostimulation systems may be associated with adverse events including heating sensation, discomfort, blistering not caused by heating, skin irritation, or redness near the implanted neurostimulator during or after recharging. Subjects should check for skin irritation or redness near the neurostimulator during recharging.

11.1.1.5 **Study-Specific Risks**

As part of the study, subjects may be asked to have fluoroscopic or X-ray images taken. This may be beyond what is standard of care. A slight increase in cancer risk may exist for people exposed to radiation. Following the fluoroscopic procedure, the skin area exposed to the x-rays could react to produce an effect similar to a sun burn. A skin reaction, if it occurs at all, could show up from a few hours to a few weeks after the procedure, and usually goes away on its own.

Parameters used during the study may not be effective, which could result in an increased level of pain. Additionally, study parameters may cause an uncomfortable level of stimulation in acute or ambulatory settings.

MDT18036 Version 3.0

Page 42 of 66

Depending on the programmed parameters the subject was using when they entered the study, it is possible subjects with rechargeable devices may need to recharge more frequently during one or more treatment periods. Depending on their programming parameters the subject was using when they entered the study, it is possible that subjects with non-rechargeable devices may require a revision surgery of their neurostimulator sooner than if they did not enter the study.

There may be additional risks related to this study, other than the ones described, that are not yet known.

[figure not shown]
11.1.1.6 Additional Risks and Information

Additional information including precautions, warnings, and contraindications is included within the packaged labeling of each system component.

11.2 Risk Minimization

At any time during the study, subjects will be able to turn their device OFF using their patient programmer or recharger. Furthermore, a subject has the right to withdraw from the study at any time and for any reason (eg, due to insufficient pain relief).

For patients with non-rechargeable devices, the programming settings will be closely monitored to minimize the risk of battery depletion that is sooner than their expected battery duration. It is the duration of the estimated battery duration with the proposed settings will be calculated by using the application on the clinician tablet. This time will be compared to the patient's baseline estimated battery duration. For newly implanted patients (i.e., subjects that have less than two weeks of stimulation after implantation), the baseline estimated battery duration will be calculated based on appropriate parameters and intensities used for standard-of-care programming. For patients with stable programming settings, the baseline estimated battery duration will be calculated using their baseline programming settings.

Medtronic Business Restricted

MDT18036 Version 3.0 Page 43 of 66

If the subject is determined not to be a candidate, the subject will be programmed per standard of care and exited from the study.

the estimated battery longevity will be

calculated compared to the current study settings. The programmer will compare the estimated battery duration of any new settings to that of the current programming settings and monitor current battery level.

At any point in the course of the study, the patient may exit the study and continue with their standard of care for any reason, including concern over battery usage. In addition, the current battery level and estimated battery life of the neurostimulator will be reviewed to further minimize the likelihood of any unexpected battery usage.

Further mitigations reside in careful construction of the study. This includes selecting an appropriate patient population via inclusion/exclusion screening and closely monitoring subject progress and events reported for the study. Additionally, qualified investigators with proper SCS therapy experience will be selected, which includes trained personnel to perform any additional imaging taken as a part of the study.

Labeling that contains precautions, warnings, and contraindications, as well as instructions on the use of the devices are available to investigators who may provide this information to subjects.

11.3 Potential Benefits

[figure not shown]
There may be no direct medical benefit to subjects participating in the study. During the study subjects will have increased interaction with physicians or medical staff compared to routine clinical care, which may provide some indirect health benefits. The SCS settings used during this study may reduce subjects' pain intensity, return subjects to a more fully functional status, improve their quality of life, or limit unwanted side effects. The SCS settings used in this study may also prolong the battery longevity of non-rechargeable neurostimulators or increase time between recharging for rechargeable devices. These benefits cannot be guaranteed due to the investigational nature of this study.

The primary anticipated benefit of this study is to help Medtronic with the understanding of SCS therapy and assist with the design of future studies and product improvements. The information gathered from this study could also help clinicians optimize therapy for their patients.

11.4 Risk-Benefit Rationale

Subjects participating in this study will be exposed to risks from commercial SCS therapy that have been deemed, through existing PMA approval, to be outweighed by the benefits of treating chronic, intractable pain within approved indications. Additional risks that exist due to participation in the study, including reduced efficacy and uncomfortable stimulation have been minimized by mitigations within the study design, and will be properly communicated to potential subjects. The additional risk of earlier

MDT18036 Version 3.0 Page 44 of 66

battery depletion resulting in device replacement for patients with non-rechargeable devices has been minimized by estimating the battery longevity and will be properly communicated to potential subjects.

12. Adverse Events and Device Deficiencies

12.1 Adverse Events

AE definitions are provided in Table 12-1. Each event is defined according to International Organization for Standardization (ISO) 14155. Where the definition indicates "device", it refers to any device used in the study. This might be the device under investigation, or any market-released component of the system.

Adverse Event (AE) information will be collected from the time the subject has been enrolled until they are discontinued from the study. AE information will be reported to Medtronic on an adverse event eCRF, one for each Adverse Event.

Only those AEs which are related to the following will be collected:

- The SCS system and accessories (device-related)
- SCS therapy (therapy-related)
- SCS procedure (procedure-related)

Each event will be classified according to 5 different levels of causality using the following terms:

- Not Related
- Unlikely
- Possible
- Probable
- Causal

Only events that are classified as possible, probable or causal are considered to be related for data analysis.

It is the responsibility of the investigator to identify the occurrence of adverse events and device deficiencies and to ensure all required information is accurately documented on the eCRF. See the eCRFs for the information to be reported for each adverse event.

Documented pre-existing conditions are not considered adverse events unless the severity of the condition has worsened and is related to the implanted SCS system, procedure, accessories, or therapy.

Events that are not reportable for this study are:

Lack of pain relief

MDT18036 Version 3.0 Page 45 of 66

- o Pain symptoms will be collected as part of the efficacy measures
- Sensation of stimulation (paresthesia)
 - Sensation of stimulation (e.g. tingling, buzzing) will not be reported as this may occur as part of this therapy. Exception: Sensation or stimulation events that are uncomfortable to the subject (e.g. shocking, jolting) will be reported.
- Adverse events unrelated to
 - o Implanted SCS system, accessories or surgical procedure
 - Spinal cord stimulation therapy

For adverse events that require immediate reporting, initial reporting may be done by phone, fax, or email, or on the eCRF by completing as much information as is available. The adverse event eCRF must be completed as soon as possible.

The clinical course of each adverse event must be followed until the adverse event is resolved or the subject is in a stable condition. "Ongoing" adverse events must be assessed at each study visit. The adverse event eCRF should be updated when there is a change to the information provided on the form (e.g. change in intervention, outcome, relatedness, etc.).

12.2 Device Deficiency

The DD definition is provided in Table 12-1. DD information will be collected throughout the study and reported to Medtronic on a device event eCRF, one for each device deficiency. Note that DD that results in an AE to the subject should be captured as an AE only.

[figure not shown]
12.3 Processing Updates and Resolution

For any changes in status of a previously reported adverse event or DD (i.e. change in actions taken, change in outcome, change in relatedness), information needs to be updated on, or added to the original AE or DD form. All AEs must be followed until the AE has been resolved, is unresolved with no further actions planned, the subject dies or exits the study, or until study closure, whichever occurs first.

In the event that a subject is exited from the study prior to study completion, all efforts should be made to continue following the subject until all unresolved system or procedure related AEs, as classified by the investigator, are resolved, unresolved with no further actions planned, or 30 days post study exit, whichever occurs first.

At the time of study exit, all collected adverse events that are unresolved must be reviewed and an update to the original AE must be reported.

MDT18036 Version 3.0 Page 46 of 66

12.4 Definitions/Classifications

Table 12-1: Adverse Event and Device Deficiency Definitions

MDT18036 Version 3.0 Page 47 of 66

	General				
Adverse Event (AE):	Any untoward medical occurrence, unintended disease or injury, or untoward clinical signs (including abnormal laboratory findings) in subjects, users or other persons, whether or not related to the investigational medical device. **NOTE 1: This definition includes events related to the investigational medical device or the comparator. **NOTE 2: This definition includes events related to the procedures involved. **NOTE 3: For users or other persons, this definition is restricted to events related to investigational medical devices.				
Adverse Device Effect (ADE):	Adverse event related to the use of an investigational medical device. NOTE 1: This definition includes adverse events resulting from insufficient or inadequate instructions for use, deployment, implantation, installation, or operation, or any malfunction of the investigational medical device. NOTE 2: This definition includes any event resulting from use error or from intentional misuse of the investigational medical device.				
Serious Adverse Event (SAE):	Adverse event that a) led to death, b) led to serious deterioration in the health of the subject, that either resulted in 1) a life-threatening illness or injury, or 2) a permanent impairment of a body structure or a body function, or 3) in-patient or prolonged hospitalization, or 4) medical or surgical intervention to prevent life-threatening illness or injury or permanent impairment to a body structure or a body function, c) led to foetal distress, foetal death or a congenital abnormality or birth defect. NOTE: Planned hospitalization for a pre-existing condition, or a procedure required by the CIP, without serious deterioration in health, is not considered a serious adverse event.				
Serious Adverse Device	Adverse device effect that has resulted in any of the consequences				
Effect (SADE):	characteristic of a serious adverse event.				
Device Deficiency (DD):	Inadequacy of a medical device with respect to its identity, quality, durability, reliability, safety or performance. NOTE: Device deficiencies include malfunctions, use errors, and inadequate labeling.				

MDT18036 Version 3.0 Page 48 of 66

Malfunction:	Failure of an investigational medical device to perform in accordance with its				
	intended purpose when used in accordance with the instructions for use or CIP.				
Use Error:	Act or omission of an act that results in a different medical device response than intended by the manufacturer or expected by the user. NOTE 1: Use error includes slips, lapses, and mistakes. NOTE 2: An unexpected physiological response of the subject does not in itself				
	constitute a use error.				
	Relatedness				
Device Related	An AE that results from the presence or performance of any component of the system.				
(includes all implantable					
components and features, associated introduction tools,	Neurostimulator-related: An AE that results from the presence or performance (intended or otherwise) of the neurostimulator.				
operational and installed software and programmers as	Lead-related: An AE that results from the presence or performance (intended or otherwise) of the lead.				
defined in the CIP, see Section 7.1)	Extension-related: An AE that results from the presence or performance (intended or otherwise) of the extension.				
	External Study Device-related: An AE that results from the presence or performance (intended or otherwise) of an external study device (e.g. programmer, ENS).				
Therapy Related	Event related to therapy delivery by device. Normally therapy-related events resolve when the device is turned off or reprogrammed. This category should not include events that resulted from a malfunction of the device (i.e. hardware-related events).				
Procedure Related	An AE that occurs due to any procedure related to the implantation or surgical modification of the system.				
	Seriousness				

Page 49 of 66 MDT18036 Version 3.0

Serious Adverse Event	AE that led to any of the following				
(SAE)	 a) death, b) serious deterioration in the health of the subject, users or other persons as defined by one or more of the following: a life-threatening illness or injury, or a permanent impairment of a body structure or a body function, including chronic disease, or in-patient or prolonged hospitalization, or medical or surgical intervention to prevent life-threatening illness or injury or permanent impairment to a body structure or a body function, fetal distress, fetal death or a congenital abnormality or birth defect including physical or mental impairment 				
	NOTE 1: Planned hospitalization for a pre-existing condition, or a procedure required by the CIP, without serious deterioration in health, is not considered an SAE.				
Serious Adverse Device	Adverse device effect that has resulted in any of the consequences				
Effect (SADE)	characteristic of a serious adverse event.				
Causality					

MDT18036 Version 3.0 Page 50 of 66

Medtronic

Not Related	Relationship to the device or procedures can be excluded when: - the event is not a known¹ side effect of the product category the device belongs to or of similar devices and procedures; - the event has no temporal relationship with the use of the investigational device or the procedures; - the serious event does not follow a known response pattern to the medical device (if the response pattern is previously known) and is biologically implausible;			
	 the discontinuation of medical device application or the reduction of the level of activation/exposure - when clinically feasible – and reintroduction of its use (or increase of the level of activation/exposure), do not impact on the serious event; the event involves a body-site or an organ not expected to be affected by the device or procedure; the serious event can be attributed to another cause (e.g. an underlying or concurrent illness/ clinical condition, an effect of another device, drug, treatment or other risk factors); the event does not depend on a false result given by the investigational device used for diagnosis², when applicable; harms to the subject are not clearly due to use error; In order to establish the non-relatedness, not all the criteria listed 			
	above might be met at the same time, depending on the type of device/procedures and the serious event. ¹When the event is not a known side effect of the product category the device belongs to or of similar devices and procedures, generally is considered "not related". Yet, the unexpected effect shall not be excluded from evaluation and reporting. ²If an investigational device gives an incorrect diagnosis, the patient might, for example, receive an unnecessary treatment and incur all the risks that accompany that treatment, or might be incorrectly diagnosed with a serious disease. In other cases, the patient might not receive an effective treatment (thereby missing out on the benefits that treatment would confer) or might not be diagnosed with the correct disease or condition.			
Unlikely	The relationship with the use of the device seems not relevant and/or the event can be reasonably explained by another cause, but additional information may be obtained.			
Possible	The relationship with the use of the investigational device is weak but cannot be ruled out completely. Alternative causes are also possible (e.g. an underlying or concurrent illness/ clinical condition or/and an effect of another device, drug or treatment). Cases were relatedness cannot be assessed or no information has been obtained should also be classified as possible.			

MDT18036 Version 3.0 Page 51 of 66

Medtronic	

Probable	The relationship with the use of the investigational device seems relevant and/or the event cannot reasonably explained by another cause, but additional information may be obtained.				
Causal Relationship	The serious event is associated with the investigational device or with procedures beyond reasonable doubt when: - the event is a known side effect of the product category the device belongs to or of similar devices and procedures; - the event has a temporal relationship with investigational device use/application or procedures; - the event involves a body-site or organ that the investigational device or procedures are applied to; - the investigational device or procedures have an effect on; - the serious event follows a known response pattern to the medical device (if the response pattern is previously known); - the discontinuation of medical device application (or reduction of the level of activation/exposure) and reintroduction of its use (or increase of the level of activation/exposure), impact on the serious event (when clinically feasible); - other possible causes (e.g. an underlying or concurrent illness/clinical condition or/and an effect of another device, drug or treatment) have been adequately ruled out; - harm to the subject is due to error in use; - the event depends on a false result given by the investigational device used for diagnosis¹, when applicable; - In order to establish the relatedness, not all the criteria listed above might be met at the same time, depending on the type of device/procedures and the serious event.				
	might, for example, receive an unnecessary treatment and incur all the risks that accompany that treatment, or might be incorrectly diagnosed with a serious disease. In other cases, the patient might not receive an effective treatment (thereby missing out on the benefits that treatment would confer), or might not be diagnosed with the correct disease or condition.				

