10.13 Imaging

Subjects may be asked to have fluoroscopic or X-ray images taken of their implanted lead(s) as part of the study, unless imaging taken prior to the subject's enrollment or as part of their standard of care are available and allow for the anatomical location of the active contacts to be defined. If the subject does not have adequate imaging available, imaging may be performed, at no more than 1 visit throughout the study, to obtain anterior/posterior and lateral fluoroscopy or X-ray views that allow for the anatomical location of the active contacts to be defined. Standard of care images taken during the subject's participation, but not required by the study, may also be collected.

[figure not shown]

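### AEs caused by imaging done for the study fall outside the AE collection rule, although the protocol names imaging among its study-specific risks

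*Protocol*

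**What the plan says.** **Imaging.** Protocol 10.13 lets the study ask for fluoroscopic or X-ray views of the implanted leads when existing images do not show where the active contacts lie: "If the subject does not have adequate imaging available, imaging may be performed, at no more than 1 visit throughout the study". Section 10.18.6 adds that images may be collected at a single visit when they matter for the parameters under test.

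**Named risk.** Section 11.1.1.5, under study-specific risks, says that this imaging may exceed standard of care. It mentions a slight increase in cancer risk from radiation and a skin effect: "Following the fluoroscopic procedure, the skin area exposed to the x-rays could react to produce an effect similar to a sun burn". The stated onset runs from hours to weeks, and the reaction is said usually to resolve unaided.

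**Collection rule.** Protocol 12.1 and SAP 7.10 both state: "Only those AEs which are related to the following will be collected". The three items that follow are the SCS system and accessories, SCS therapy, and the SCS procedure. Protocol 10.19 gives the same three.

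**Definitions in Table 12-1.**
- Device related: "An AE that results from the presence or performance of any component of the system"
- Therapy related: "Event related to therapy delivery by device"
- Procedure related: "An AE that occurs due to any procedure related to the implantation or surgical modification of the system"

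**Exclusion list.** Section 12.1 also has a list that opens "Events that are not reportable for this study are". Its last item covers AEs unrelated to the implanted system, its accessories, the surgical procedure or stimulation therapy.

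**The concern.** Restricting AE collection to related events is an ordinary choice in a post-market study of marketed devices. What makes it look wrong here is that the restriction leaves out a harm arising from participation itself. A subject imaged only because the study asked for it is exposed to something that the protocol describes as possibly beyond standard care, and the protocol names a consequence that could appear during follow-up. The rule then makes that consequence not reportable as a study AE.

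At stake is what the safety summaries can say about the burden of taking part. Section 11.2 counts close monitoring of reported events among the risk mitigations, which cannot work for an event that sites are told is not reportable. Section 13 provides no events committee or data monitoring committee that might look at such events separately.

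**Working it through.** The plan gives no figure on this point, so there is none to reproduce. The check sets the provisions against each other and then illustrates the possible size.

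**1. Does an imaging-related AE fit a collected category?** Take a skin reaction that the investigator attributes to fluoroscopy done for the study.

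| Category | Scope in Table 12-1 | Does the event fit? |
|---|---|---|
| Device related | Components of the SCS system, including external items such as the programmer | No. Imaging equipment is not part of the system described in 7.1 |
| Therapy related | Stimulation delivered by the device | No |
| Procedure related | Implanting or surgically modifying the system | No. Subjects are already implanted (7.1), and imaging the lead is not surgery |

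**2. Does the exclusion list leave room?** No. The item in 12.1 qualifies procedure as surgical, which agrees with Table 12-1.

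**3. Does the general AE definition rescue it?** Table 12-1 defines an AE broadly and notes that events from the procedures involved are included. That settles what counts as an AE. Section 12.1 then settles which AEs are collected, and it is narrower.

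**4. Do other routes exist?**

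| Route | What it could pick up | Does it enter the AE tables as imaging harm? |
|---|---|---|
| IRB requirements (12.5.1, 12.5.2) | Whatever the local IRB requires | No |
| Death notification (12.6) | Any death; an AE form only if device, procedure or therapy related | No |
| Exit reason (10.22; SAP 7.1.1) | An AE that leads to exit, listed among discontinuations | No |
| Medical history updates (Table 10-1) | New conditions as they occur | No |
| Visit form (10.9) | Non-reportable events that may affect pain reporting | No |
| Default to possible (Table 12-1) | Events whose relatedness cannot be assessed, such as redness near the neurostimulator | Enters as device related, so misattributed |

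**5. How many events could be involved?** This is illustration only, because the documents give neither the number imaged nor a harm rate. Let n be the number imaged for the study and p the true risk per subject, both assumed. Expected events = n × p, and P(at least one) = 1 − (1 − p)^n. The values of n are 30 (the group size in the precision example), 90 (a quarter of 360) and 360 (the enrolment ceiling).

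| n | p = 0.5% | p = 2% | p = 5% | P(at least one) at 2% |
|---|---|---|---|---|
| 30 | 30 × 0.005 = 0.15 | 0.6 | 1.5 | 0.455 |
| 90 | 0.45 | 1.8 | 4.5 | 0.838 |
| 360 | 1.8 | 7.2 | 18 | 0.999 |

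The bottom row supposes that every subject is imaged, which 10.13 and 10.18.6 make unlikely. For the skin reaction, n should count fluoroscopy only, since 11.1.1.5 ties the reaction to that technique.

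**6. How should silence in the tables be read?** It cannot be read as 0 events in n. The exact two-sided 95% upper limit for an observed 0/n is 1 − 0.025^(1/n): 11.6% for n = 30, 4.0% for n = 90 and 1.0% for n = 360. None of these limits would be valid here, because the events were not eligible for collection. The rate is simply not estimable.

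**The case against.** The strongest reply is that the loss is small. Imaging is optional, conditional on inadequate existing images, limited to one visit and perhaps unused in some cohorts. The skin reaction usually resolves by itself, and a radiation-induced cancer would hardly appear during follow-up under any rule. Pain scores are untouched. All of this stands, and it limits how much weight the point can bear.

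A second reply is textual. Section 12.1 says that device, where a definition uses the word, means any device used in the study, which might seem to take in imaging equipment. But that sentence goes on to speak of the device under investigation and market-released system components, and the collected category is the SCS system and its accessories. The reading does not close the gap.

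A reader might also infer several stronger things that the documents do not support:

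- *That sites are forbidden to report such an event, even a serious one.* Section 12.1 makes it not reportable as a study AE. It does not stop reporting to an IRB, notification of a death or recording an exit reason.
- *That the plan will report an imaging-harm rate of zero.* Protocol 14.5 and SAP 7.10 tabulate device-, procedure- and therapy-related events. No visible table has an imaging row or denominator, so the harm goes unreported rather than reported as zero.
- *That imaged subjects have no AE collection.* They remain under collection for the three stated categories. Only imaging-attributed events are lost.
- *That imaging is the only procedure the study adds.* Much of Section 10 and most row labels in Table 10-1 are blacked out, so this cannot be known.
- *That the risk-benefit statement would be falsified.* Section 11.4 is a prospective rationale. It reports no event rates, and nothing says that it will be revised from the safety tables.

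**Conclusion.** The point holds as a gap in the collection rule. The protocol names a harm from study-directed imaging, and the rule in protocol 10.19 and 12.1 and SAP 7.10, read with Table 12-1, keeps an AE attributed to that imaging out of the study AE data and the planned safety tables. The visible sections agree with one another on this, and no visible clause closes the gap. Blacked-out text could in principle do so.

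The size cannot be derived from the documents. That few events are probably lost is a judgement resting on the optional, single-visit, conditional nature of the imaging. The primary objective is not affected. The case for acting is that the harm comes from participation and the correction is cheap, not that many events would be missed.

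**What to change.** Make AEs related to study-directed imaging collectable in protocol 10.19, 12.1 (including the not-reportable list), Tables 12-1 and 12-2, and SAP 7.10. Either of two wordings would do: widen procedure related to include imaging done for the study, or add a separate study-procedure category. Study-directed describes the imaging better than study-required, since it is optional.

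Whichever wording is chosen, these AEs should stay identifiable in the tables and be reported with the number of subjects imaged for the study. Merging them with implant or revision events over all enrolled subjects would hide the rate. For example, one event among 30 imaged is 1/30 = 3.3%, while over 360 enrolled it is 1/360 = 0.3%. The denominator requires the data to separate images taken for the study from prior or standard-of-care images, both of which 10.13 also allows.

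The cost is a wording amendment, one more relatedness option on the AE eCRF and a few more AE reports. If the imaging record does not already show why images were taken, one further field is needed. No change to clinical management is involved.
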